STUDY PROTOCOL

Study name	Understanding Non-Response in Spine Fusion Surgery
Principal investigator	[name], MPH
Project lead	[name], MPH
Document Date	2/6/2019

CONTENTS

Study protocol	1
Abstract.....	2
Objective	2
Design.....	2
Recruitment Workflow Notes	2
Original Recruitment Design	3
Data Collection Design	4
Methods.....	4
Likely impact	5

ABSTRACT

There is considerable debate about the effectiveness of spine fusion surgery for degenerative disc disease (DDD) and other diagnoses related to chronic back pain. As many as 1-in-3 patients who undergo spine fusion do not report improvements in pain or functional status. Additionally, there are currently no evidence-based selection criteria to help surgeons determine which patients will respond to spine fusion surgery and which will not benefit.

The goal of this study was to better understand which patients are more likely to benefit from spinal fusion surgery. The Comparative Effectiveness Research Translation Network (CERTAIN) Spine Fusion Study partnered with spine surgery clinics to invite patients to participate in research activities designed to identify the impact of spine fusion surgery on the outcomes that matter most to patients. As part of this study, patients took surveys before and after their spine fusion surgery, and shared elements of their medical records for review. CERTAIN anticipated that this study would produce a paradigm that clinicians can use with patients to determine whether spine fusion surgery is right for them and identify any modifiable risk factors that may impact their response to surgery.

OBJECTIVE

Determine patient characteristics associated with non-response among patients undergoing lumbar fusion for DDD.

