STATISTICAL ANALYSIS PLAN

Study name	Understanding Non-Response in Spine Fusion Surgery
Principal investigators	[name], MPH
Project lead	[name], MPH
Document Date	2/6/2019
Team conducting analysis	[name], MS [name], MPH
Version	3

AIM 1

We will assess baseline covariates with respect to the primary outcome, the Oswestry Disability Index (ODI) failure to achieve at least a 15% improvement (minimal important clinical difference as established by the Food and Drug Administration [FDA]) in the ODI score which ranges from 0 to 100 where 0 indicates not disability and 100 indicates complete disability when comparing baseline to six months after surgical procedure, reporting proportions for categorical variables and means and other measures of central tendency for continuous variables. We will use a multivariate logistic regression model with robust standard errors to evaluate these covariates and the primary outcome. A latent class analysis will be used to identify clusters of traits (e.g., patients with depression, anxiety, and catastrophizing) that tend to be grouped together within patient subtypes. This technique assumes there are distinct patterns and that individuals can be grouped into a small number of clusters representing each outcome path (the “latent classes”). The association between clusters and non-response will be described using logistic regression models accounting for repeated testing. As a sensitivity analysis, we will repeat the latent class analysis on the raw percentage change of the primary outcome measure to examine the robustness of variables that define latent classes. We will also conduct a sensitivity analysis looking for different degrees of change in the primary outcome beyond the 15% threshold defined by the FDA. We will also conduct a missing data analysis to describe and characterize enrolled participants who do not provide further outcome measures due to attrition. We will conduct sensitivity analyses using 10-fold multiple imputation to assess the robustness of the results. We will create an imputation model with variables found to be predictive of missingness and data will be imputed to create 10 complete data sets. The results will then be combined across data sets with the using STATA (i.e., MI) statistical software packages.

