As a sensitivity analysis, we will repeat the latent class analysis on the raw percentage change of the primary outcome measure to examine the robustness of variables that define latent classes. We will also conduct a sensitivity analysis looking for different degrees of change in the primary outcome beyond the 15pts threshold defined by the FDA. We will also conduct a missing data analysis to describe and characterize enrolled participants who do not provide further outcome measures due to attrition. We

will conduct sensitivity analyses using 10-fold multiple imputation to assess the robustness of the results.

We will assess baseline covariates with respect to ODI non-improvement at 60 days, reporting proportions for categorical variables and means and other measures of central tendency for continuous variables. A multivariate logistic regression model with robust standard errors will be used to evaluate these covariates and the primary outcome: ODI non-Improvement at 60 days.

Use a latent class analysis to identify clusters of traits (e.g., patients with depression, anxiety, and catastrophizing) that tend to be grouped together within patient subtypes. This technique assumes there are distinct patterns and that individuals can be grouped into a small number of clusters representing each outcome path (the “latent classes”). The association between clusters and non-response will be described using logistic regression models accounting for repeated testing.

AIM 2

For responders and non-responders, we will perform a descriptive analysis of radiographic characteristics and compare proportions for categorical variables and means for continuous variables. We will explore the associations between radiographic measures and non-response using conditional logistic regression models, as appropriate for matched case-controls studies with multiple controls.

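### Fixing multiple imputation at 10 data sets leaves borderline results dependent on the random seed if the fraction of missing information is about 0.2 or more

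*SAP*

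**What the plan says.** The main Aim 1 analysis is a regression of ODI non-response on baseline covariates: "We will use a multivariate logistic regression model with robust standard errors to evaluate these covariates and the primary outcome". For losses to follow-up, the SAP plans to describe "enrolled participants who do not provide further outcome measures due to attrition" and then to re-analyse by multiple imputation: "We will conduct sensitivity analyses using 10-fold multiple imputation to assess the robustness of the results". The number of data sets is explicit: "data will be imputed to create 10 complete data sets". The content of the imputation model is given only as "We will create an imputation model with variables found to be predictive of missingness", and pooling is to be done in Stata. The 10-fold figure appears again later in Aim 1, where the block of sensitivity analyses is repeated.

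Neither document states an expected attrition rate, a sample size, a significance level, a random seed, a tolerance for Monte Carlo error, or a rule for raising the number of imputations. The SAP also does not say how the imputed results will be compared with the main results when robustness is judged.

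**The concern.** A robustness check compares two sets of coefficients, intervals and perhaps p-values: those from the main model (presumably complete cases, although the SAP does not say so) and those from the imputed data. With few imputations, part of any difference is noise from the imputation draws. The usual justification for 10 data sets is that the pooled point estimate is nearly fully efficient. That does not show that another run would give the same coefficient, standard error or p-value.

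Imputation is the only planned re-estimation of the associations under attrition; the other missing-data analysis is descriptive. The Rationale in the protocol lists many candidate characteristics, so several could be borderline. If one of them changes between the two models, the plan offers no means of telling a missing-data effect from seed noise.

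**Working it through.** **Inputs from the documents.** Number of imputations m = 10 (SAP, Aim 1). The SAP does not derive this figure, so there is no calculation to reproduce.

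**Assumptions.** FMI from 0.1 to 0.5, because no rate is given. FMI is not the attrition rate itself; it also depends on how well the imputation model predicts what is missing. A two-sided 0.05 cut-off is used only as a yardstick, since the SAP states no significance level.

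**Step 1: movement of the pooled coefficient.** Scale the total variance with unlimited imputations to 1, so that the between-imputation variance is B = FMI and the within-imputation variance is W = 1 − FMI. The seed-to-seed standard deviation of the pooled coefficient, in units of its standard error, is √(FMI/m). With m = 10:

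- FMI 0.1: √0.01 = 0.10
- FMI 0.2: √0.02 = 0.14
- FMI 0.3: √0.03 = 0.17
- FMI 0.5: √0.05 = 0.22

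With m = 50 the values at FMI 0.2, 0.3 and 0.5 are 0.06, 0.08 and 0.10.

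**Step 2: movement of the standard error.** Its coefficient of variation is approximately FMI/√(2(m − 1)). With m = 10, √18 = 4.243, which gives 0.3/4.243 = 7.1% and 0.5/4.243 = 11.8%. With m = 50, √98 = 9.899, which gives 3.0% and 5.1%.

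**Step 3: movement of the p-value.** For each simulated seed, draw the pooled estimate with variance FMI/m about its unlimited-imputation value, and draw B as FMI times a chi-square on m − 1 degrees of freedom divided by m − 1. Then apply Rubin's rules: T = W + (1 + 1/m)B, referred to a t distribution with (m − 1)(1 + W/((1 + 1/m)B))² degrees of freedom. One million seeds per setting gave these shares with p above 0.05:

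| FMI | p = 0.03, m = 10 | p = 0.03, m = 50 | p = 0.01, m = 10 |
|---|---|---|---|
| 0.1 | 4% | below 0.1% | below 0.1% |
| 0.2 | 16% | 0.4% | about 0.2% |
| 0.3 | 25% | 2% | 1.5% |
| 0.5 | 37% | 9% | about 9% |

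The p in each column heading is the value that unlimited imputations would give. For p = 0.03 and m = 10, the central 95% of seeds run from 0.013 to 0.07 at FMI 0.2, from 0.010 to 0.09 at 0.3 and from 0.005 to 0.14 at 0.5. With m = 50 the ranges are 0.021 to 0.044, 0.018 to 0.050 and 0.014 to 0.061.

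**Step 4: validity and average width.** Under no association, the same scheme with m = 10 rejects in about 5% of runs at FMI 0.2, 0.3 and 0.5, so the test is calibrated. The average interval half-width is 2.7% above the unlimited-imputation value at FMI 0.3 and about 5.7% above it at 0.5; with m = 50 the excess is 0.5% and 1.0%.

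**Step 5: imputations needed.** Requiring √(FMI/m) ≤ 0.10 gives m ≥ 100 × FMI: 10, 20, 30 and 50 at FMI 0.1, 0.2, 0.3 and 0.5. Ten imputations meet this tolerance only if FMI is 0.1 or less.

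**The case against.** There is a good case for leaving the plan alone, and much of it stands.

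- **No attrition rate is given.** A reader might infer that attrition is substantial and the imputed analysis therefore unstable. The documents do not support that: they mention attrition without a figure, and at FMI 0.1 the effect is small.
- **No criterion is stated.** A reader might infer that robustness will be judged by p-values, so that another seed could reverse the verdict. The SAP sets no such rule and no 0.05 cut-off. What survives is that the coefficient moves too, so a comparison of odds ratios is also blurred, though less visibly.
- **The inference is sound.** Rubin's rules already carry the finite-m noise through the (1 + 1/m)B term and the t reference, and Step 4 confirms calibration. The efficiency of the point estimate, 1/(1 + FMI/m), is 0.98 at FMI 0.2 and 0.95 at FMI 0.5.
- **Clear results are stable.** At p = 0.01 at least 91% of seeds stay below 0.05 even at FMI 0.5. The p = 0.03 case was chosen because it lies near the cut-off.
- **The stakes are limited.** This is a sensitivity analysis in a study whose protocol calls it exploratory, under Likely Impact.

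These arguments make the point conditional and minor. They do not supply a reason for fixing the number at 10 before the amount of missing information is known.

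**Conclusion.** The point holds as a cheap improvement of low severity. If FMI is about 0.2 or more, 10 imputations leave borderline associations noticeably dependent on the seed: for an unlimited-imputation p of 0.03, between 16% (FMI 0.2) and 37% (FMI 0.5) of seeds cross an assumed 0.05 line. The pooled coefficient shifts by 14% to 22% of its standard error over the same range. If FMI is 0.1 or lower, or the result is well away from the cut-off, little changes.

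The FMI values and the cut-off are assumptions, not figures from the documents. It would go too far to conclude that the planned imputation is invalid, biased or bound to mislead. The defect is a fixed number of imputations with no check on whether it is enough.

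**What to change.** In SAP Aim 1, replace the figure of 10 data sets, and both mentions of 10-fold imputation, with at least 50 imputed data sets. Add that the Monte Carlo error of each pooled coefficient, √(B/m), will be reported, and that m will be raised until this error is at most 10% of the coefficient's standard error, which means m of about 100 × FMI. Starting from 50 meets the rule for FMI up to 0.5, so the increase comes into play only above that.

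Record the random seed so that the run can be repeated; a fixed seed does not itself reduce Monte Carlo error. It would also help to say in one sentence how the imputed and main results will be compared.

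The cost is a few words in the SAP and some computing time. No new data are needed, and the primary regression is unaffected.

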Rationale: *A patient's sense of activation in managing their health, loci of control, tendency towards catastrophizing, social support, satisfaction with work, self-perceived quality of life, expectations, general mental health, anxiety and depression, and extent of critical medication (e.g., opioids, sleeping aids) use have been associated with clinical outcomes and self-perception of health status. These parameters have not been well studied among those who fail to improve with spine surgery compared to responders. Nearly all Spine SCOAP patients undergo baseline and follow up surveys of patient reported measures. We will perform a prospective cohort study adding standardized measures of personality traits and mental health and will evaluate their association with changes in function and pain at six months after surgery.*

DESIGN

Recruitment Workflow Notes

All site specific processes are in *italics*

UWMC and HMC:

- *Patients were identified from surgery schedules* (eligible if: lumbar fusion (L1-S1), over 18, English as primary language, not revision surgery, surgery date in > 10 days (not official study inclusion criteria, but needed to ensure enough time for mailers))
- *Research staff screened each patients EMR to confirm eligibility and noted in EMR disclosure log*

- Research staff sent each eligible patient a recruitment mailer containing: consent form (2), HIPAA Authorization Form (2), Study Intro Letter, Baseline survey, and a return envelope
- One week after mailer was sent, phone recruitment began; 5 calls over ~10 days
- During phone call: research staff delivered screening questions, reviewed forms, outlined which were copies for patient's own records and which to return, gave instructions on how to return
- Patient was enrolled when consent and baseline were returned via mail (HIPAA form return did not impact enrollment)

Proliance:

- Patients were identified from an automated feed delivered from Proliance IT via secure email once a week* (eligible if: lumbar fusion (L1-S1), over 18, English as primary language, not revision surgery, surgery date in > 10 days (not official study inclusion criteria, but needed to ensure enough time for mailers))
- *Research staff screened schedule for potentially eligible procedures and noted in EMR disclosure log, even though Proliance EMR was not accessed at this time*

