- Tablets: Original grant depended on patients completing CERTAIN baseline for themselves via tablet in clinic waiting room, however, patients and staff had technical difficulty with tablets
- Time: not enough time in waiting room or during rooming process to complete the CERTAIN baseline, let alone SF screening and recruitment
- Variability: each CERTAIN clinical site implemented CERTAIN at a slightly different point in their workflow (i.e. in waiting room, after rooming, after surgery scheduling, etc.) which made it difficult to provide clinic staff with guidance about how to assist with enrollment
- QI vs. Research: by not classifying SF as a multi-site study with "engaged" sites, the flexibility to allow clinic staff to actively enroll patients was lost (the exception to this is Evergreen, who had separate IRB approval for a research-only approach to enrollment, not QI)

Data Collection Design

A combination of Quality Improvement (QI) databases and research databases were used to complete the final dataset for this study. Most hospitals in Washington (WA) State participate in a novel, prospective care surveillance initiative called Spine Surgical Care and Outcomes Assessment Program (Spine SCOAP) that allows benchmarking on the indications for, processes of care, clinical outcomes and changes in patient reported outcomes (PROs) including pain and function for patients undergoing spine surgery. Spine SCOAP's analytic group, the Comparative Effectiveness Research Translation Network (CERTAIN) assesses PROs at 60-90 days, 12 and 24 months. Spine SCOAP data was obtained through CERTAIN, and research data was collected directly from patients via email or mail, rather than in the clinic as originally proposed. These surveys included additional baseline, 60-day, and 1-year characteristics and the outcome measures to the original CERTAIN surveys through the DatStat platform.

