Socio-demographic, clinical and procedural characteristics were collected from both Spine SCOAP, the CERTAIN QI surveys, and the additional research measures. Spine SCOAP data included age, zip code, race and ethnicity, insurance type, and employment status. Clinical characteristics included diagnosis and indication for surgery, preoperative comorbid conditions, known preoperative risk factors (e.g. cigarette smoking), laboratory results (e.g., albumin and HbA1c), and current medical treatments (i.e., statin, beta blocker, ACE or ARB inhibitors, therapeutic anticoagulants, steroids, and narcotic pain medication). Surgical approach (i.e. minimally invasive or open and anterior or posterior), perioperative care, fusion technique, instrumentation used and adverse clinical outcomes were also included.

METHODS

Ten CERTAIN clinics agreed to participate in the study, including: Confluence Health, Evergreen Health, Harborview Medical Center (HMC), UW Medical Center (UWMC), and six clinics from Proliance Surgeons. Within these CERTAIN clinics 28 surgeons participated. The sites represented close to 70% of

the Washington SCOAP network, with representation across public, private, and geographic healthcare settings.

INCLUSION CRITERIA:

Patients may enroll in Spine Fusion if they:

- Are receiving care from a spine surgeon at a participating clinic
- Are over 18
- Are fluent in English (able to take surveys via mail, phone, or online)
- Have lower back pain (pain for more than three months, or pain for at least half the days in the past 6 months)
- Are planning to have lumbar spine fusion surgery
- Have no history of previous spine surgery
- Are not a member of a vulnerable population
- Are able and willing to provide informed consent to participate in a research study

EXCLUSION CRITERIA:

Patients may not enroll in Spine Fusion if they:

- Are under 18 years of age
- Do not speak English (are unable to take surveys via mail, phone, or online)
- Do not have lower back pain (pain for less than three months, or not even for half the days in the last six months)
- Are not planning to have lumbar spine fusion surgery
- Have had spine surgery previously
- Are a member of a vulnerable population
- Indicate that they are unable or unwilling to provide informed consent to participate in a research study

For more information regarding the scientific background and statistical methods, see the Statistical Analysis Plan (SAP).

LIKELY IMPACT

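### SAP Aim 2 models non-response, but Aim 1 gives conflicting thresholds and time points for it, so the case group is not fixed

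*SAP*

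**What the plan says.** Aim 2 of the SAP is two sentences. The first describes radiographic characteristics by response status. The second explores their association with non-response "using conditional logistic regression models, as appropriate for matched case-controls studies with multiple controls". Neither says what makes a patient a non-responder, so the definition has to come from Aim 1.

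Aim 1 opens with a primary outcome of failing to improve by at least 15% on the ODI, "when comparing baseline to six months after surgical procedure". Later in Aim 1 the sentence on alternative thresholds appears a second time, with the threshold in points instead of per cent. The next paragraph names ODI non-improvement at 60 days as the primary outcome.

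The protocol's Rationale, under Objective, also places the outcome at six months. Its Data Collection Design says that the CERTAIN group "assesses PROs at 60-90 days, 12 and 24 months", and that the research surveys were at baseline, 60 days and 1 year.

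On design, the Rationale says "We will perform a prospective cohort study". Neither document describes a matched sub-study beyond the one phrase in Aim 2.

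**The concern.** Case status is the dependent variable of Aim 2. If the plan supports more than one definition, two analysts following it can form different case groups and report different radiographic odds ratios, with no pre-stated rule for choosing between them. The choice could then be made after results are seen. The six-month definition has a further difficulty: no listed survey supplies it.

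A second, lesser matter is that conditional logistic regression needs a set identifier. Aim 2 names the model without saying what the sets are or how controls are chosen.

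**Working it through.** **1. The definitions side by side**

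| Place | Time point | Threshold | Status |
|---|---|---|---|
| Protocol, Objective (Rationale) | six months | none | outcome of interest |
| SAP Aim 1, opening | six months | 15% | primary |
| SAP Aim 1, repeated sensitivity text | none | 15 points | threshold of the primary outcome |
| SAP Aim 1, 60-day paragraph | 60 days | none | primary |
| SAP Aim 2 | none | none | responder or non-responder |

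Surveys listed in the protocol's Data Collection Design: CERTAIN at 60-90 days, 12 and 24 months; research at baseline, 60 days and 1 year. None is at six months.

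**2. When the two thresholds agree**

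The SAP gives the ODI range as 0 to 100. If 15% means 15 points on that scale, the thresholds are the same. If it means change relative to baseline B, the requirement is 0.15 × B points:

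- B = 40: 6.0 points
- B = 50: 7.5 points
- B = 60: 9.0 points
- B = 100: 15.0 points

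On the relative reading they coincide only where 0.15 × B = 15, that is B = 100. The documents give no baseline ODI; 40 to 60 is an assumption.

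**3. How many patients would change group**

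Assume improvement is normal with mean m = 10 to 20 points and SD s = 15 to 20 (not in the documents). The share who are cases under 15 points but responders under a relative 15% is

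D = Φ((15 − m)/s) − Φ((0.15B − m)/s).

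- Largest: B = 40, m = 10, s = 15. D = 0.631 − 0.395 = 0.236.
- Middle: B = 50, m = 15, s = 20. D = 0.500 − 0.354 = 0.146.
- Smallest: B = 60, m = 20, s = 20. D = 0.401 − 0.291 = 0.110.

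So D is about 11% to 24%. Over the same grid the non-response share is 17.5% to 48.0% under the relative rule and 36.9% to 63.1% under 15 points.

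**4. The time point**

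The documents give nothing on how 60-day and six-month response relate, so the effect of that choice cannot be sized.

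**5. Secondary: the matched design**

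Neither document gives matching factors, a control ratio, control selection or the handling of unmatched cases, or says whether all radiographs are read. The cohort supplies at most (1 − p)/p controls per case at non-response p, without reuse. That is 2.0 at p = 1/3, the upper background figure in the protocol Abstract ("As many as 1-in-3 patients who undergo spine fusion do not report improvements in pain or functional status"), and 4.0 at an assumed p = 0.20.

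A simulation shows what could follow *if* all radiographs were read and complete 1:2 sets were then drawn within clinic. It takes ten clinics from the protocol's Methods and assumes N, the 1:2 ratio, a log odds ratio of 0.5 per SD and a between-clinic SD of 0 to 0.5. At p = 1/3, 17-24% of patients go unused at n = 300 and 24-30% at n = 150. Against conditioning on clinic in everyone, the model-based variance of the log odds ratio is 1.24-1.32 and 1.35-1.42 times as large. At p = 0.20 about 41-46% go unused. Most of that comes from the assumed ratio: 1:2 sets can use at most 3 × 0.20 = 60% of patients, so 40% are lost before any clinic constraint.

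**The case against.** On the definitions, the strongest reply is that the conflict is editorial. The opening sentence of Aim 1 states the 0-100 range next to the 15%, so 15 scale points is a natural reading, and the later change to points may only make that explicit. The 60-day paragraph could likewise be a secondary analysis mislabelled. Both readings are possible, but the SAP does not state either. Aim 1 also plans a sensitivity analysis on raw percentage change, so a relative reading is not far-fetched. The 60-day label cannot be dismissed as a slip when 60 days is a listed survey and six months is not. These are Aim 1 inconsistencies that would affect Aim 2 under any model; that is why the repair belongs in Aim 1.

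On the matching, a reader might infer that conditional logistic regression is the wrong model for a cohort. The documents do not support that. Aim 2's wording signals a matched sub-study, a matched case-control study nested in a cohort is legitimate, and the model is standard for one. Clinic could also serve as the set.

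A reader might also take the simulation as the cost of the plan. It is not: neither document proposes 1:2 sets or says that all radiographs are read. If only a subset is read, matching may be a sensible economy.

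Nor does the absence of imaging from the protocol's list of collected data show that there is no source. The list does not claim to be complete, and the Abstract says that patients shared parts of their medical records.

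**Conclusion.** The definition of a case is contradictory as written: two time points each carry the primary label, the earlier-stated one has no listed survey, and the threshold appears in two units. This rests on the text alone. The 11% to 24% reclassification applies only to the relative reading of 15%, under the assumed baseline and improvement distributions; it is zero if 15% means scale points.

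The missing sets, ratio, control selection and reading rule are incomplete specification. The simulation illustrates one possible design and carries no weight in judging severity.

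The protocol's Likely Impact section calls the study exploratory, and Aim 2 is worded as exploration. The matching gap leaves the Aim 1 result untouched. The plan should be corrected, but nothing here supports a stronger demand.

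**What to change.** **Main change, SAP wording only.**

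- In Aim 1, reconcile threshold and time point into one primary definition of non-response. State whether the threshold is in scale points or relative to baseline.
- Tie the definition to an assessment that the study collects. If a six-month assessment exists, add it to the protocol's Data Collection Design.
- Label any other time point secondary.
- In Aim 2, cite that one definition.

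**Secondary change, also wording.** State in Aim 2 whether radiographs are read for all participants or a subset.

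- If a subset: keep conditional logistic regression and state the matched sets and matching factors, the control ratio, how controls are selected and what happens to unmatched cases.
- If all: analyse everyone with a radiograph, for example by conditioning on clinic, instead of drawing fixed-ratio sets.

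Neither branch requires extra radiograph reads.
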